## Document History Clinical Investigation Plan CP-00003

Version	Description	Release Date
A	Initial Release	27Mar2020
B	
The following changes have been implemented:
 
 
- Change of number of investigational sites
 
- Added a new site in Denmark
 
- Change of study start date
 
- Clarification of the primary performance endpoint
 
- Clarification of the primary safety endpoint
 
- Additional information to the device description
 
- Deletion of the physical examination and the vital signs
 
- Clarification of anticipated adverse events with the CathVision Cube® System and the EP-procedures
 
- Addition of malfunctions and device deficiencies from the CathVision Cube® System
 
- Removal of the DMSB because it is not mandatory for this study
 
- Improvement of the CIP structure
 
- Implementation of the appendix 1-3 in the CIP
 
- Minor wording changes
 
	24Jun2020
C	
The following changes have been implemented:
 
 
- Adaption of study duration due to COVID-19 restrictions including start-and end date
 
- Correction of timelines for Final Study Report
 
- Added email address of PI [name]
 
- Administrative Changes
 
	24Mar2021

---

## STUDY SYNOPSIS

Title	An evaluation of the safety and performance of the CathVision Cube® System
Investigational Device	
The CathVision Cube® System and accessories is an electrophysiology EP recording system to be used in EP procedures to acquire, amplify, digitize, stream atrial and ventricular intracardiac electrophysiology signals during cardiac electrophysiology procedures.
 
Intended Use	Acquire, amplify, digitize, stream atrial and ventricular intracardiac electrophysiology signals during cardiac electrophysiology procedures.
Objective	The primary objective is to evaluate the safety and technical performance of the CathVision Cube® System. The secondary objective is to benchmark the intracardiac electrogram signal quality compared to commercially available systems in subjects undergoing elective assessment and ablation of cardiac arrhythmias (EP procedure).
Study Design	
A prospective, multi-center, open-label, single arm study to evaluate the safety and technical performance of the CathVision Cube® System.
 
Subjects who are indicated to undergo EP procedure and meet all inclusion criteria will be enrolled in the study and undergo the EP procedure. Intracardiac signals will be passively recorded using CathVision Cube® System in parallel with the commercial (CE marked) EP recording system. The investigational device will not be used for direct clinical care decisions or therapy. The EP procedure will be guided by the study site standards of care.

Sample size	Up to 30 subjects shall be enrolled in the study.
Investigational Sites	Two (2) investigational sites in Europe.
Study Duration / Follow-up Period	
Study enrolment is planned from October 2020 to July 2021
 
Subjects will have clinical follow-up prior to hospital discharge.


Primary Performance Endpoint
	
The Primary Performance Endpoint of the study will be evaluated as technical success of CathVision Cube® System to collect and record intracardiac signals during EP procedures with focus on:
 
 
• Recording low-voltage electrograms
 
• Logging time for arrhythmia termination
 
• Assessing the improved signal quality (baseline noise level peak-to-peak)
 
• Assessing compatibility of CathVision Cube® System with a commercially available 3D mapping systems Biosense Webster Cart3 and GE Cardiolab. In addition, site standard of care available intracardiac catheters will be used.
 

Secondary Safety Endpoint
	
The Secondary Endpoint should demonstrate no or minimal adverse events or device malfunctions reported with the use of the CathVision Cube® System.

Enrollment Criteria
	
Inclusion Criteria
 
Eligible subjects will meet all of the following inclusion criteria:
 
 
1. Patient indicated by investigator for catheter ablation or diagnostic electrophysiology procedure.
 
2. Male or non-pregnant female aged <math>\geq 18</math> years. Female subjects of childbearing potential must have a negative pregnancy test (per site standard test) within 7 days prior to index procedure.
 
3. Able and willing to directly provide informed consent.
 
 
Exclusion Criteria
 
Eligible subjects will not meet any of the following exclusion criteria:
 
 
1. Subject inability to understand or refusal to sign informed consent.
 
2. Pregnant or nursing subjects and those who plan pregnancy in the period up to 1 month following the index procedure.
 
3. Current participation in another investigational drug or device study that interferes with this study
 
4. Subject is a prisoner
 
5. Subjects who, in the opinion of the physician, are not candidates for this study.
 

---

## ABBREVIATIONS

ADE	Adverse Device Effect
AE	Adverse Event
AF	Atrial Fibrillation
ASD	Atrial Septal Defect
β-HCG	Beta Human Chorionic Gonadotropin
CA	Competent Authority
CIP	Clinical Investigatn Plan
CPK	Creatinine Phosphokinase
CS	Clinically Significant
CVA	Cerebrovascular Accident
CRA	Clinical Research Associate
CRF	Case Report Form
EC	Ethics Committee
ECG	Electrocardiogram
EGM	Electrogram
EP	Electrophysiology Procedure
GCP	Good Clinical Practices
GDPR	General Data Protection Regulation
LV	Left Ventricular
NCS	Not Clinically Significant
PFO	Patent Foramen Ovale
PI	Principal Investigator
PV	Pulmonary Vein
RF	Radiofrequency
SADE	Serious Adverse Device Effect
SAE	Serious Adverse Event
SW	Software
TIA	Transient Ischemic Attack
TEE	Transesophageal Echocardiogram
TTM	Trans telephonic Monitoring
UADE	Unanticipated Adverse Device Effect

---

# 1. Introduction

## 1.1. Cardiac Electrophysiology

Of the total worldwide population, 1% and 2% of rural and urban areas suffer from cardiac arrhythmia, respectively. Approximately 15% of patients do not respond to drug treatment and need a device-based interventional treatment. As a result, there is a great need of cardiac arrhythmia ablation. Today, however, the exact identification of the mechanism of the arrhythmia and subsequent successful ablation treatment are challenging for physicians. The three most prevalent arrhythmias (“complex arrhythmias”) for catheter ablation are atrial fibrillation, atrial tachycardia and ventricular tachycardia.

## 1.2. Intracardiac electrophysiology signals during cardiac electrophysiology procedures

Cardiac electrograms are generated by the potential (voltage) differences recorded at two recording electrodes during the cardiac cycle. All clinical electrogram recordings are differential recordings from one source that is connected to the anodal (positive) input of the recording amplifier and a second source that is connected to the cathodal (negative) input. Unipolar recordings are obtained by positioning the exploring electrode in the heart and the second electrode (referred to as an indifferent electrode) distant (theoretically an infinite distance) from the heart such that it has little or no cardiac signal. Bipolar recordings are obtained by connecting two electrodes that are exploring the area of interest to the recording amplifier. At each point in time the potential generated is the sum of the potential from the positive input and the potential at the negative input. The potential at the negative input is inverted, and thus subtracted from that at the positive input. Because the far-field signal is similar at each instant in time, it is largely subtracted out, leaving the local signal. In a homogeneous sheet of tissue, the initial peak of the bipolar signal coincides with depolarization beneath the recording electrode. [2]

## 1.3. Rationale for this Clinical Investigation

Electrograms and their interpretation are a key tool for electrophysiologists to target ablation sites, and are acquired from electrodes on intracardiac diagnostic catheters and from surface ECG. Beside the dominant noise contributor of 50/60Hz from mains power line, there are noise contributors from stimulation, ablation and defibrillation artifacts that disturb the clear view of electrophysiological signals. Stimulation artifacts today are a result of (poor) software filter design, whereas ablation artifacts are mostly a hardware problem from the high energy exposure on the ablation tip electrode that is also used for measurements.

Baseline noise peak-to-peak levels below 15 $\mu$ V in bipolar recordings and below 30 $\mu$ V in unipolar recordings would be considered best-in-class. Bipolar recordings between adjacent band electrodes are the most commonly used and practically they are often “derived bipolar”. This means they are individual signals first amplified against a different but common reference, and then subtracted from each other. Unipolar recordings are important for advanced algorithms, such as 3D mapping and rotor mapping for atrial fibrillation. The unipolar reference is most often Wilson Central Terminal (WCT), but it can also be a distant intracardiac electrode.

---

Electrograms are usually sampled at 1 to 2kHz, and bandpass filtered at 30 to 500Hz for bipolar and 0.5 to 300Hz for unipolar recordings. 64 to 160 channels are the typical capacity of recording systems today.

In the operating room, other devices and technologies are present: 3D mapping (triangulation of catheter tip position with impedance- and magnetic technology, <0.2 gauss), fluoroscopy/X-ray, RF generator, cryo gas station, stimulator, saline coolant pump for ablation catheter RF-tip irrigation, hemodynamics, magnetic catheter steering (0.08T).

It is not unusual to defibrillate the patient to cardiovert them from an arrhythmia. It is not unusual that patients have implanted defibrillators (ICDs).

It is CathVision's goal to develop a new electrophysiology recording system with improved signal quality particularly of unipolar recordings, with fast pacing and defibrillation recovery times, and with minimal or reduced RF ablation artifacts. The reduction in noise and artifacts will allow for better diagnosis and delivery of advanced ablation therapy in arrhythmia patients.

## 2. Device Description

[figure not shown]
The CathVision Cube® System is an electrophysiology (EP) recording system used in EP procedures as a tool to monitor, display, and record signals of the heart and cardiac arrhythmias. The CathVision Cube® System includes the following items:

- EP amplifier (EPAMP)
- Pin box cable assembly for connection of catheters
- Surface ECG cable
- Data cable to host computer
- Recording system software (RECORDER SW)
- Host computer (PC) and monitors

Additional information involving the device and its components, including all preclinical and clinical test results, can be found in the Investigator's Brochure or in the Instructions for Use.

### 2.1. Signal Processing Overview

The main hardware amplifier of the CathVision Cube® System is the EPAMP, which acquires signals from third-party catheters and sensors connected to the subjects. It then sends the signals to the CathVision Cube® System, which has a software program called the RECORDER SW that visualizes the signals to the user and provides the users a way to interactively analyze them. The following figure illustrates this signal pathway.

There are no parts of the CathVision Cube® System that may come into contact with subjects body or body fluids. There are no medicinal products, human or animal tissues or their derivatives, or other biologically active substances used in the device.

---

## 2.2. Device Labelling

The investigational device does not have a CE label, therefore the study device will be labelled “for investigational use only”.

Each manufactured investigational device is assigned a unique serial or lot number that is printed on the device labeling, providing a means of traceability. A device accountability log will be used to track the use of devices in the study. The serial number will be recorded on each case report form

## 3. Risk-Benefit Analysis

There are no known risks to the potential subjects specifically associated with the use of the CathVision Cube® System.

Potential subject risks include adverse events and potential product failures similar to commercially available EP recording systems, with a similar likelihood of occurrence.

Potential device malfunctions and potential user errors have been identified in the Hazard Analysis and Failure Modes and Effects Analysis exercises conducted in accordance with ISO 14971. These are technical complications that may occur with the devices. Mitigating steps to address each of the potential device malfunctions and potential user errors have been implemented to reduce the risks as low as possible. No residual risks remain that are higher than the risks associated with the use of currently available conventional cardiac electrophysiology and catheter ablation tools. A list of device deficiencies and malfunction are defined in section 7.7 of this document.

The anticipated adverse events associated with cardiac electrophysiology procedures include events reported in the literature related to catheter procedures, events identified in the risk and hazard analyses, and events associated with percutaneous interventions, and therefore represent the risks associated with participation in the study. A list of anticipated adverse events is defined in Section 7.6 of this document. Each adverse event or device effect will be evaluated in detail as described in Section 7 of this document.

The CIP is designed for parallel data collection during electrophysiology study and investigator diagnostic decisions will be guided by an approved EP recording system. Due to this CIP design and noninvasive nature of the tested medical device there is expected a low rate of occurrence of SAEs or SADEs related to use of investigational device. CathVision personnel will be responsible for operation and installation of the tested device.

The potential patient benefits include reduction in symptomatic episodes of arrhythmia due to possible better interpretation of EP signals using the CathVision Cube® system. As the treatment will be guided by an approved EP recording system the reduction in symptomatic arrhythmia will be similar to the benefit of currently available EP recording systems.

---

## 4. Clinical Investigation Plan (CIP)

### 4.1. Study Objectives

The primary objective is to evaluate the safety and technical performance of the of the CathVision Cube® System. Secondary objective is to benchmark the intracardiac electrogram signal quality compared to commercially available systems in subjects undergoing assessment and ablation of cardiac arrhythmias.

### 4.2. Study Design

A prospective, multi-center, open-label, single arm study to evaluate the safety and technical performance of the CathVision Cube® System.

Subjects who are indicated to undergo EP procedure and meet all inclusion criteria will be enrolled in the study and undergo EP procedure using an approved EP system in conjunction with the CathVision Cube® System. Intracardiac signals will be passively recorded in parallel with the commercial (CE marked) EP recording system. The investigational device will not be used to direct clinical care decisions or therapy. The EP procedure will be guided by study site standards of care.

### 4.3. Study Duration

Study enrolment is planned from October 2020 to July 2021

Subjects will have clinical follow-up prior to hospital discharge.

### 4.4. Subject Population

Up to 30 subjects shall be enrolled in the study at a single site meeting the following study entry criteria will be treated.

#### 4.4.1. Inclusion Criteria

Eligible subjects will meet all of the following inclusion criteria:

1. Subject indicated by investigator for catheter ablation or diagnostic electrophysiology procedure.
2. Male or non-pregnant female aged  $\geq 18$  years. Female subjects of childbearing potential must have a negative pregnancy test (per site standard test) within 7 days prior to index procedure.
3. Able and willing to directly provide informed consent.

#### 4.4.2. Exclusion Criteria

Eligible subjects will not meet any of the following exclusion criteria:

1. Subject inability to understand or refusal to sign informed consent.
2. Pregnant or nursing subjects and those who plan pregnancy in the period up to 1 month following the index procedure.

- 
3. Current participation in another investigational drug or device study that interferes with this study.
  4. Subject is a prisoner.
  5. Subjects who in the opinion of the physician are not candidates for this study. Prior atrial septal defect (ASD) or patent foramen ovale (PFO) closure with a device using a transcatheter percutaneous approach.

## **5. Study Outcomes**

### **5.1. Primary Performance Outcome**

The Primary Performance Endpoint of the study will be evaluated as technical success of CathVision Cube® System to collect and record intracardiac signals during EP procedures with focus on:

- Recording low-voltage electrograms
- Logging time for arrhythmia termination / block
- Assessing the improved signal (baseline noise level peak-to-peak)
- Assessing compatibility of CathVision Cube® System with a commercially available 3D mapping systems Bioscience Webster Carto3 and GE Cardiolab. In addition, site standard of care available intracardiac catheters will be used.

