## **8. Statistical Methods**

### **8.1. Sample Size Calculation**

This study is intended to demonstrate safety and performance of the device. As a result, no formal statistical hypothesis was applied to derive the sample size. A drop-out rate is expected to be low due to acute and low risk profile of CIP.

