## **9.5. Sponsor Responsibilities**

All information and data sent to the Sponsor concerning subjects or their participation in this study will be considered confidential. Only authorized Sponsor or Sponsor's Designee will have access to these confidential records. Authorized regulatory personnel have the right to inspect and copy all records pertinent to this study. Study data collected during this study may be used by the Sponsor for the purposes of this study, publication, and to support future research and/or other business purposes. All data used in the analysis and reporting of this study will be without identifiable reference to specific subject name and will be pseudonymized. The Sponsor or authorized Designees of the Sponsor may be present at the EP procedures to provide technical and study specific assistance and shall assist with the collection of recorded technical data via the use of Technical Source Forms. The CathVision Cube® System is password protected and only the Sponsor is allow to work with the study device. Any data collected by the Sponsor's Designee will be verified and counter signed by the Investigator. The Sponsor's Designee will not:

- Practice medicine
- Provide medical diagnosis or treatment to subjects

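### Does the noise item of the primary performance endpoint need a stated comparator or level for the word 'improved'?

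*Protocol*

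**What the plan says.** Section 5.1 states that the primary performance endpoint "will be evaluated as technical success of CathVision Cube® System". The same sentence goes on to say at what: collecting and recording intracardiac signals during the procedure. Four focus items follow. The third is "Assessing the improved signal (baseline noise level peak-to-peak", and the synopsis has nearly the same words: "Assessing the improved signal quality (baseline noise level peak-to-peak". Neither place gives a reference system, a level, or a choice between bipolar and unipolar recordings.

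Two possible references stand elsewhere in the protocol:

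- The rationale in section 1.3 remarks: "Baseline noise peak-to-peak levels below 15 $\mu$ V in bipolar recordings and below 30 $\mu$ V in unipolar recordings would be considered best-in-class".
- Section 4.1 says: "Secondary objective is to benchmark the intracardiac electrogram signal quality compared to commercially available systems". The data for this come from the design in section 4.2: "Intracardiac signals will be passively recorded in parallel with the commercial (CE marked) EP recording system". Section 5.3.4 adds that the two sets of recordings are compared after the procedure.

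On analysis, section 8.1 says "This study is intended to demonstrate safety and performance of the device" and then at once that no formal hypothesis was used to derive the sample size. Section 8.2 plans summary statistics for continuous and categorical variables and sets no statistical criterion for stopping the study.

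**The concern.** 'Improved' is a comparative word, and here nothing is named to compare with. Read with the phrase about technical success, the item looks like a pass/fail test whose standard was never written down. It could mean Cube noise below the 1.3 level, Cube noise below the parallel commercial recording, or a description only. The second reading is what 4.1 calls secondary, so a primary item appears to be worded as the secondary comparison.

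At stake would be a success claim settled after the data are known. The study is open-label, and section 9.5 says "only the Sponsor is allow to work with the study device". If the two references gave opposite answers on the same recordings, the more favourable one could be chosen.

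**Working it through.** The protocol states no threshold, power or success rate for noise, so there is no figure of its own to reproduce. Two questions can be checked: could the two references disagree, and does the plan ever use them to make a success call?

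**1. Could they disagree?** Rule A: Cube bipolar noise below 15 µV (section 1.3). Rule B: Cube noise below that of the parallel commercial system. The documents give no noise values, so every value here is assumed. Subject-level noise is taken as lognormal with medians mC (Cube) and mK (commercial), common log-SD s and within-subject correlation ρ:

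- P(A) = Φ( ln(15/mC) / s )
- P(B) = Φ( ln(mK/mC) / ( s·√(2(1−ρ)) ) )

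Each probability times 30 gives the expected number of subjects.

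| mC / mK (µV) | s, ρ | Rule A, of 30 | Rule B, of 30 |
|---|---|---|---|
| 14 / 12 | s = 0.2, ρ = 0.8 | 19.0 | 3.3 |
| 14 / 12 | s = 0.4, ρ = 0 | 17.1 | 11.8 |
| 20 / 30 | s = 0.2, ρ = 0.8 | 2.3 | 30.0 |
| 20 / 30 | s = 0.4, ρ = 0 | 7.1 | 22.9 |

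First row: ln(15/14)/0.2 = 0.345 and Φ(0.345) = 0.635, which gives 19.0. For rule B, ln(12/14)/(0.2·√0.4) = −1.22 and Φ(−1.22) = 0.111, which gives 3.3.

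These two pairs of medians were picked to conflict. A separate simulation (CV 30%, ρ = 0.5, nine assumed pairs of medians) includes pairs where the totals match: 12/15 gives 23 and 23, and 18/15 gives 8 and 8. Individual subjects are still classified differently in 24% and 27% of cases there. Over all nine pairs that share runs from 22% to 73%. So disagreement is possible, and its frequency depends entirely on the assumed values.

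**2. Does the plan make a success call on noise?** The relevant sections, side by side:

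| Section | What it fixes | Noise pass/fail rule? |
|---|---|---|
| 5.1, synopsis | Technical success in collecting and recording signals; noise is a focus item to be assessed | No |
| 1.3 | Background on what would count as very good noise performance | No; no objective, endpoint or analysis cites it |
| 4.1 | Benchmark against commercial systems, secondary | No |
| 4.2, 5.3.4 | Parallel recording, compared after the procedure | No |
| 8.1 | No formal hypothesis | No |
| 8.2 | Descriptive summaries | No |

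Rule A enters only if a background remark is promoted to a criterion. Counting subjects below a cut-off is likewise a rule found nowhere in the protocol. Without them there are no two success calls to set against each other.

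**3. Bipolar or unipolar.** A level between 15 and 30 µV meets the 1.3 figure if unipolar and misses it if bipolar. That is not an ambiguity: section 1.3 assigns one level to each recording type. Which channels are tabulated is ordinary analysis detail.

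**The case for a change.** The best case for a change is that what a primary item is judged against belongs to the endpoint's definition and is not detail to leave to an analysis plan. The protocol chose a comparative word, ranked the obvious comparison as secondary, and speaks both of technical success and of demonstrating performance. If noise is only to be described, one line would say so at no cost in patients or data, and would close the door on choosing a standard later.

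Part of this stands. 'Improved' presupposes the result, and it is unclear whether the commercial comparison serves the primary endpoint, the secondary objective or both.

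The rest carries less weight. One noise measurement can serve both objectives without contradiction. The remark in 8.1 about demonstrating performance is followed directly by the statement that no hypothesis was applied. The restriction in 9.5 concerns who operates the device, not who interprets the endpoint. The same section has the investigator verify and countersign data collected by the sponsor's designee, although that does not itself settle which standard applies. Of the possible remedies, neutral wording leaves every reported number as it is. Adopting 15/30 µV would give the study a pass/fail threshold that it does not otherwise have and for which the protocol offers no justification as a criterion.

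**Conclusion.** No change follows. The observation is accurate: neither 5.1 nor the synopsis says what the noise is improved against. But this is a loaded word and an unwritten detail in a descriptive study of up to 30 subjects, and an analyst would fill it sensibly. The natural output is peak-to-peak noise for the Cube and for the parallel commercial system, by recording type, with their within-subject comparison. Any reader can then hold those figures against the commercial system or against the levels in 1.3.

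The effect on that output of rewording the item is nil. The divergent counts in the working show only what is logically possible. They rest on assumed medians, spread and correlation, and on a threshold the plan does not adopt. The conclusion rests on reading technical success as success in collecting and recording signals, which is how the full sentence in 5.1 runs, and on section 8 being descriptive. It would differ if the sponsor meant to declare pass or fail on noise, and the protocol sets no rule for doing so.
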